5.1.2.2 Procedures for Recording Adverse Events

Investigator should use correct medical terminology/concepts when recording adverse events in the Adverse Event eCRF. Colloquialisms and abbreviations should be avoided.

Only one adverse event term should be recorded in the event field of the eCRF.

See Appendix 5 for further specific instructions regarding:

- IRRs
- Diagnosis versus signs and symptoms
- Adverse events occurring secondary to other adverse events
- Persistent or recurrent adverse events
- Abnormal laboratory values
- Abnormal vital sign values
- Abnormal liver function tests
- Deaths
 - All events with an outcome or consequence of death should be classified as serious adverse events and reported to the Sponsor immediately. In certain circumstances, however, suspected adverse reactions with fatal outcome may not be subject to expedited reporting (see Section 5.4). All deaths that occur during the protocol-specified adverse event reporting period, regardless of relationship to study medicine, must be recorded in the Adverse Event eCRF and immediately reported to the Sponsor.
- Worsening of pre-existing medical conditions
- Lack of therapeutic efficacy
- Hospitalization or prolonged hospitalization
- Overdoses, misuses, abuses, off-label use, occupational exposure, or medication error
- Quality defects, falsified medicinal products and product complaints
- Drug interactions

5.1.3 Reporting Requirements from HCP to Sponsor

5.1.3.1 Immediate Reporting Requirements from HCP to Sponsor

Certain events require immediate reporting to allow the Sponsor and the regulatory authorities to take appropriate measures to address potential new risks associated with the use of the medicine. The investigator must report such events to the Sponsor immediately; under no circumstances should reporting take place more than 24 hours after the investigator learns of the event. The following is a list of events that the investigator must report to the Sponsor within 24 hours after learning of the event, regardless of relationship to study medicine:

- Serious adverse events
- Non-serious adverse events of special interest
- Accidental pregnancy occurred during the study (for additional information see Section 5.1.3.5)

The investigator must report new significant follow-up information for these events to the Sponsor immediately (i.e., no more than 24 hours after becoming aware of the information). New significant information includes the following:

- New signs or symptoms or a change in the diagnosis
- Significant new diagnostic test results
- Change in causality based on new information
- Change in the event's outcome, including recovery
- Additional narrative information on the clinical course of the event

For reports of serious adverse events and non-serious adverse events of special interest, including follow-up, investigator should record all case details that can be gathered immediately (i.e., within 24 hours) in the Adverse Event eCRF and submit the report via the electronic data capture (EDC) system. A report will be generated and sent to Roche Drug Safety by the EDC system. In the event that the EDC system is temporarily unavailable, refer to Section 5.1.3.4.

Investigator must also comply with local requirements for reporting serious adverse events to the local health authority and IRB/EC.

5.1.3.2 *Medical Monitors and Emergency Medical Contacts*

To ensure the safety of study participants, access to the Medical Monitor is available 24 hours per day, 7 days per week. An Emergency Medical Call Center will also be available 24 hours per day, 7 days per week. Details will be provided separately. The Emergency Medical Call Center will connect the investigator with an Emergency Medical Contact, provide medical translation service if necessary, and track all calls. Contact information, including toll-free numbers for the Emergency Medical Call Center vill connects.

5.1.3.3 Reporting Requirements for Non-Serious Adverse Events

For all non-serious adverse events, including follow-up reports, the investigator must record all case details that can be gathered within 30 calendar days of learning of the event on the adverse event section of the eCRF.

Ocrelizumab—F. Hoffmann-La Roche Ltd 57/Protocol MN42988, Version 3

5.1.3.4 If EDC System Is Temporarily Unavailable

In the event that the EDC system is temporarily unavailable, a completed paper reporting form and fax coversheet should be faxed/scanned to Roche Drug Safety or its designee immediately (i.e., no more than 24 hours after learning of the event) or within 30 calendar days for non-serious adverse events if not adverse events of special interest, using the fax number or email address provided to investigator.

Once the system is available again, all information should additionally be entered and submitted via the EDC system.

5.1.3.5 Reporting Requirements for Pregnancies, Abortions/Congenital Anomalies/Birth Defects

Pregnancies

All pregnancies in women enrolled in this study should have been previously reported to the Sponsor as spontaneous pregnancy reports by following the standard pharmacovigilance reporting process for post-marketing pregnancy cases. This should be done by a neurologist at the time of learning of the patient's pregnancy. In case a pregnant woman enrolled in the study becomes accidentally pregnant again during the study, she will remain on study and discontinue treatment with commercial ocrelizumab until pregnancy completion. She and her subject infant should continue with all study assessments. The investigator should complete the Global Clinical Trial Pregnancy Form and submit it to the Sponsor or its designee immediately (i.e., no more than 24 hours after learning of the accidental pregnancy), either by faxing or by scanning and emailing the form using the fax number or email address provided to investigators. Pregnancy should not be recorded on the Adverse Event eCRF. The investigator will submit to the Sponsor a Clinical Trial Pregnancy Reporting Form when updated information on the course and outcome of the pregnancy becomes available. Any serious adverse events associated with the accidental pregnancy during the study (e.g., an event in the fetus, an event in the mother during or after the pregnancy, or a congenital anomaly/birth defect in the child) should be reported on the Adverse Event section of the eCRF.

Abortions

Pregnant women who experienced a spontaneous abortion will be excluded from the study at enrollment, scheduled at gestational Week 24–30; see Section 4.1.2, exclusions related to obstetric and gynecological health. Thus, the reporting of spontaneous abortion as serious adverse event is exempted in this study, while it should be reported as medical history on the study eCRF Medical History page, if a spontaneous abortion occurred in previous pregnancy.

If a therapeutic or elective abortion was performed because of an underlying maternal or embryofetal toxicity, the toxicity should be classified as an SAE, recorded on the Adverse Event eCRF, and reported to the Sponsor immediately (i.e., no more than 24 hours after learning of the event; see Section 5.1.3.1). A therapeutic or elective

Ocrelizumab—F. Hoffmann-La Roche Ltd 58/Protocol MN42988, Version 3

abortion performed for reasons other than an underlying maternal or embryofetal toxicity is not considered an AE.

In addition, therapeutic or elective abortion should be reported as pregnancy outcomes on the study eCRF Pregnancy page and reported to the Sponsor immediately (i.e., no more than 24 hours after learning of the event; see Section 5.1.3.1).

Congenital Anomalies/Birth Defects

Any congenital anomaly/birth defect in a child born to a female patient exposed to the medicine should be classified as a serious adverse event, recorded in the adverse event section of the eCRF, and reported to the Sponsor immediately (i.e., no more than 24 hours after learning of the event; see Section 5.1.3.1).

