4.1.1 Inclusion Criteria

Women must meet the following criteria for study entry:

- An Informed Consent Form (ICF) for participation of the maternal subject and her unborn (for collection of blood samples, infant demographics and adverse event data) is signed and dated by the subject. Where applicable, the written ICF with respect to the infant is also signed and dated by the holder of parental rights as designated by the maternal subject.
- Able and willing to comply with the study protocol, in the Investigator's judgment.
- Age 18–40 years, inclusive, at screening.
- Have a diagnosis of MS or CIS (in line with the locally approved indications).
- Currently pregnant with singleton pregnancy at gestational Week \leq 30 at enrollment.

Note: Gestational age will be determined by LMP and first trimester ultrasound so long as there is less than 1 week's difference in the projected due date. If there is over 1 week's difference, then the ultrasound alone will be used. For cases where the LMP is not known, then the earliest ultrasound will be used. For cases of in vitro fertilization (IVF), the projected dates from the IVF procedure will be preferentially used.

- Documentation that first (12-week) and second (18–20-week) obstetric ultrasound (prenatal screening) has been conducted before enrollment.
- Documentation that the last exposure to ocrelizumab occurred up to 6 months before the LMP before the woman became pregnant OR during the first trimester of pregnancy (up to gestational Week 13 inclusive).

Note: Exposure to ocrelizumab includes administration of an initial split dose of two 300 mg infusions (in 250 mL 0.9% sodium chloride) separated by 14 days for women initiating treatment with ocrelizumab, or a single 600 mg infusion (in 500 mL 0.9% sodium chloride) for women already on treatment with ocrelizumab.

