4.1.2 Exclusion Criteria

Women who meet any of the following criteria will be excluded from study entry:

- Last exposure to ocrelizumab > 6 months before the woman's LMP or later than the first trimester of pregnancy (i.e., after gestational Week 13).
- Gestational age at enrollment > 30 weeks.
- Non-singleton pregnancy.
- Received the last dose of ocrelizumab at a different posology other than per the local prescribing information.
- Social circumstances (e.g., home relocation), that may preclude a woman from participating in the study.

Exclusions Related to Obstetric and Gynecological Health

- Lack of access to ultrasound prenatal care as part of standard clinical practice.
- Women in whom aneuploid disorders or genetic disorders that cause major congenital malformations have been detected during first trimester prenatal screening (e.g., ultrasound, amniocentesis, genetic testing, nuchal translucency screening, chorionic villus sampling), or in whom any fetal anomalies (i.e., fetal biometry, fetal anatomy) have been detected during the morphology scan at around or before gestational Week 18–20.
- Documented history of disorders associated with adverse pregnancy outcomes, including but not limited to, the following:
 - History of preterm birth (gestational age < 37 weeks) for any indication with or without fetal malformations.
 - History of spontaneous abortion (miscarriage) after the first trimester (i.e., after gestational Week 13).
 - History of stillbirth (defined as fetal loss at gestational age > 22 weeks).
 - History of pre-eclampsia/eclampsia.
 - History of a cervical pathology or intervention which may increase the risk of cervical incompetence (e.g., history of cervical cerclage, prior cervical conization or prior loop electrosurgical excision procedure [LEEP]).
- Prior or current history of any other gynecological or obstetric disease considered by the investigator to be associated with a high risk of adverse pregnancy outcomes in the current pregnancy.

Exclusions Related to General Health

- Lack of peripheral venous access.
- Pre-pregnancy body mass index (BMI) > 35 kg/m².
- Any concomitant disease that may require chronic treatment with systemic corticosteroids or immunosuppressants during the course of the study.

- Prior or current history of primary or secondary immunodeficiency, or woman in an otherwise severely immunocompromised state. The woman may be re-screened and included if condition resolves.

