- Duration of the most recent DMT as continuous and categorical (≤6 months, >6 and ≤12 months, >12 and ≤24 months, >24 months)
- Time (months) from last DMT to first ocrelizumab infusion before enrollment
- Time (months) from last DMT to LMP

Prior Ocrelizumab Use

- Number and percentage of women received ocrelizumab in 3-month interval of before/during pregnancy (3-6 prior LMP, 0-3 month prior to LMP, 1st trimester)
- Time (months) between last ocrelizumab before LMP and LMP
- Time (months) between LMP and last ocrelizumab after LMP
- Received ocrelizumab after LMP (yes, no)
- Duration (months) of ocrelizumab therapy prior to enrolment
- Duration of ocrelizumab therapy prior to enrolment (≤6 months, >6 and ≤12 months, >12 and ≤24 months, >24 months)

Prior Medications

Prior medication (defined as treatment ended before LMP) and concurrent medications (defined as treatment started on or after the LMP) will be summarized, by frequency tables according to the Anatomic Therapeutic Chemical (ATC) classification system using the WHO Drug dictionary.

Baseline Disease Characteristics

- Baseline EDSS continuous and categorical (<2.5 vs ≥2.5)
- Baseline EDSS distribution: count and percent of patients corresponding to each observed score of EDSS at baseline
- Presence of any clinically significant abnormalities from the neurological examination (Yes, No)
- Type of neurological abnormality (disability progression independent of relapse, MS relapse, signs or symptoms suggestive of Progressive Multifocal Leukoencephalopathy, Other)

Obstetric and Gynecological History

- History of previous pregnancies (Yes/No)
- Number of previous pregnancies (1, 2, 3, 4, >4)
- Previous pregnancy outcome (Full term live birth, preterm live birth, spontaneous abortion, still birth, therapeutic abortion, elective abortion, ectopic pregnancy, unknown)

- Gestational Age (Weeks) as continuous and categorical (<23, 23-27, 28-32, 33-36, ≥37)
- History of adverse pregnancy outcomes (Yes/No)
- History of obstetrical complications during previous pregnancies (Yes/No)
- Type of obstetrical complication during previous pregnancies
- Reason for termination (if terminated)

Medical History

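### Protocol 5.1.3.5 gives two conflicting instructions for a miscarriage in a repeat pregnancy on study, and the reason given for the SAE exemption does not match Section 4.1.2

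*Protocol*

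**What the plan says.** Protocol 5.1.3.5 treats the subject in two adjacent paragraphs.

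- **Pregnancies.** A second pregnancy is foreseen: "In case a pregnant woman enrolled in the study becomes accidentally pregnant again during the study, she will remain on study". It is notified on a separate pregnancy form, updated with course and outcome, and the pregnancy itself is kept off the AE eCRF. Adverse events are handled differently, in a sentence that begins "Any serious adverse events associated with the accidental pregnancy during the study (e.g., an event in the fetus, an event in the mother during" and that directs such events to the AE section of the eCRF. Birth defects in the child are a further example there.
- **Abortions.** The premise is "Pregnant women who experienced a spontaneous abortion will be excluded from the study at enrollment, scheduled at gestational Week 24–30", with a reference to Section 4.1.2. The conclusion is "Thus, the reporting of spontaneous abortion as serious adverse event is exempted in this study". The sentence continues "while it should be reported as medical history on the study eCRF Medical History page, if a spontaneous abortion occurred in previous pregnancy".

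The criterion in Section 4.1.2 is narrower than that premise: "History of spontaneous abortion (miscarriage) after the first trimester (i.e., after gestational Week 13"). SAP 4.3.1 also expects enrolled women with earlier miscarriages, since it tabulates "Previous pregnancy outcome (Full term live birth, preterm live birth, spontaneous abortion, still birth" and further categories.

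Two other provisions matter. Protocol 5.1.3.1 makes an accidental pregnancy reportable within 24 hours and sets the same limit for significant follow-up, including a changed outcome. Protocol 4.3.2.1 allows commercial ocrelizumab to be resumed after birth, and 3.1.4 follows mother and infant until the infant is about 13 months old.

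**The concern.** The exemption is worded for the whole study, but its justification is an eligibility screen. A screen at Weeks 24–30 can make miscarriage of the pregnancy being screened irrelevant. It cannot prevent miscarriage of a pregnancy conceived later, which the same section expects may happen and which may follow postpartum ocrelizumab.

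A site with such a case has a general instruction to record SAEs of the repeat pregnancy and a specific instruction not to report spontaneous abortion as one. Sites may reasonably choose differently. What is at stake is whether the event is classified as serious and reaches the SAE outputs, in a study whose safety objectives cover mothers given ocrelizumab.

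**Working it through.** No design figure is involved. The check sets the passages side by side, with a small calculation for scale.

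**1. Does the stated reason match Section 4.1.2?** No. Section 5.1.3.5 describes exclusion of women who have had a spontaneous abortion. Section 4.1.2 excludes only a history of loss after Week 13, so women with earlier losses are eligible. The medical-history instruction in 5.1.3.5 and the previous-outcome categories in SAP 4.3.1 both presuppose such women. A charitable reading is that a woman whose index pregnancy has already miscarried cannot be enrolled. That is true, but it concerns only the index pregnancy.

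**2. Can the reason reach a repeat pregnancy?** No. That pregnancy begins after enrollment, so no enrollment criterion applies to it.

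**3. What do the two paragraphs require for a miscarriage in a repeat pregnancy?**

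| Provision | Instruction |
|---|---|
| 5.1.3.5, Pregnancies | SAEs of the accidental pregnancy, fetal events included, go on the AE eCRF |
| 5.1.3.5, Abortions | Spontaneous abortion is exempt from SAE reporting, with no limit to the index pregnancy |
| 5.1.1.2, events exempt from collection | MS-related events only; spontaneous abortion is not named |
| 5.1.3.1 | Accidental pregnancy and its significant follow-up within 24 hours |

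The first two rows conflict. The third agrees with the first. The fourth applies whichever reading a site takes.

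**4. What happens to the data if a site follows the exemption?** The event is left off the AE eCRF, or at least is not recorded there as serious. SAP 4.8.2 builds its SAE tables and listings from recorded adverse events, so the miscarriage would not appear in them. SAP 4.8.6 would not clearly recover it: its outcome types are elective abortion, therapeutic abortion, stillbirth, live birth and not applicable, and it does not mention a repeat pregnancy. The pregnancy form goes to the sponsor by fax or e-mail, and the documents do not say that its content enters the study database.

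**5. Scale.** Protocol 1.3 (Available Evidence) reports 158 spontaneous abortions among 1064 known outcomes. The outcome counts sum correctly: 809 + 72 + 158 + 6 + 2 + 17 = 1064. The rate is 158/1064 = 0.1485, in line with the stated 14.8%. The documents give no number of repeat pregnancies, so *k* = 0 to 2 is an assumption. Expected miscarriages are *k* × 0.1485, and the chance of at least one is 1 − (1 − 0.1485)^*k*.

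| *k* (assumed) | Expected | Chance of at least one |
|---|---|---|
| 0 | 0 | 0 |
| 1 | 0.15 | 15% |
| 2 | 0.30 | 27% |

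The rate is context, not a prediction. It pools pregnancies irrespective of fetal exposure status, and a further 690 were lost to follow-up or had unknown or unreported outcomes.

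**The case against.** The strongest reply is that repeat pregnancies already have their own rule. The Pregnancies paragraph covers their SAEs expressly, and the exemption is drawn from a premise about enrollment at Weeks 24–30, so in context it concerns the index pregnancy. This is probably what was intended, but the text does not say so. The exemption names spontaneous abortion specifically and applies to the study without limit, and a site may let the specific rule override the general one.

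A second reply is that the sponsor would know anyway. This stands. The 24-hour report, the 24-hour follow-up duty and the pregnancy form all operate whatever the exemption means. A reader might infer that a miscarriage after postpartum ocrelizumab would escape the sponsor's notice; the documents do not support that.

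A third is that the loose description of 4.1.2 loses no data, because earlier miscarriages are recorded as medical history. This also stands. The misdescription matters because it is the only reason offered for the exemption.

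The event is also unlikely. Protocol 1.3 notes labelled contraception for 6 months (United States) or 12 months (EU) after the last dose. That lowers the expected number, but the protocol still provides for the case.

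**Conclusion.** The contradiction is real and worth correcting. Its reach is limited to SAE classification of a miscarriage in a pregnancy that starts after enrollment, and to the completeness of the SAP 4.8.2 outputs. Under the stated assumption of 0 to 2 repeat pregnancies, 0 to 0.3 such events are expected. The primary B-cell analysis and the sample size are untouched.

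Two stronger readings are tempting and do not hold.

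- A reader might infer a similar gap in the index pregnancy, because Section 4.1.1 gives only an upper limit: "Currently pregnant with singleton pregnancy at gestational Week" 30 or earlier. However, Protocol 3.1 and the Schedule of Assessments place the combined screening and baseline visit at Weeks 24–30, and 4.5.1 requires screening evaluations to be complete before enrollment. Section 4.1.2 defines fetal loss after 22 weeks as stillbirth, which has its own category in SAP 4.8.6. No change to 4.1.1 is needed.
- A reader might express the loss as one woman in 33, or about 3% of the cohort. That presumes both that the event occurs and that the site follows the exemption. The number of repeat pregnancies is unknown, so the figure has no basis.

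**What to change.** In Protocol 5.1.3.5:

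1. Limit the exemption to spontaneous abortions in pregnancies before enrollment, recorded as medical history.
2. State that a spontaneous abortion in a pregnancy starting after enrollment follows the accidental-pregnancy SAE rule and is entered on the AE eCRF.
3. Correct the description of Section 4.1.2, which excludes only a history of loss after Week 13.

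In the SAP, report the outcome of any repeat pregnancy, including spontaneous abortion, in the safety listings.

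The cost is a few sentences in one protocol section and one addition to a listing. No eligibility criterion, study procedure or patient care changes. Because a protocol amendment goes through ethics and regulatory review (Protocol 9.7), the wording could be included in the next planned amendment.

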5.1.4 Follow-Up of Patients after Adverse Events

5.1.4.1 Investigator Follow-Up

The investigator should follow each adverse event until the event has resolved to baseline grade or better, the event is assessed as stable by the investigator, the patient is lost to follow-up, or the patient withdraws consent. Every effort should be made to follow all serious adverse events considered to be related to studied medicinal product until a final outcome can be reported.

During the study period, resolution of adverse events (with dates) should be documented in the adverse event section of the eCRF and in the patient's medical record to facilitate source data verification.

